5.7. Administration and Accountability

The investigational products will be checked on receipt as above ([Section 5.3](#)). Prior to administration, PMT-001 and PMT-002 will be allowed to thaw at room temperature (50°F - 75°F) for 30-60 minutes. Administration of PMT-001 and PMT-002 will begin within 60 minutes of thawing. Prior to administration, PMT-003 will be kept on dry ice; PMT-003 will not be thawed before administration.

As stated in [Section 5.4](#), the total time from release from frozen storage at the manufacturing facility to initiation of administration will not exceed 180 minutes for PMT-001 and PMT-002; it will not exceed 120 minutes for PMT-003.

The duration of administration will take 10 - 90 (target 30) minutes for all products. Administration of all three PMT products will be performed by a licensed physician, advanced medical practitioner, or nurse.

PMT-001 will be administered by enema using an approved enema administration kit. PMT-002 will be administered via intragastric, intraduodenal, or intrajejunal route, contingent on the presence of a pre-existing approved intragastric, intraduodenal, or intrajejunal tube. PMT-003 will be administered orally. Post-procedure monitoring will be performed as described

elsewhere. For each investigational product dose, the product identity, dose targeted for administration, the date and time administered, route of administration, subject identity, quantity of product actually administered, and quantity of product remaining will be recorded via a standard form.

5.8. *Subject Compliance Monitoring*

Post-procedure monitoring will be performed as described elsewhere ([Sections 3.1.3](#) to [Section 3.1.4](#)). For each investigational product dose, the product identity, dose targeted for administration, the date and time administered, route of administration, subject identity, quantity of product actually administered, and quantity of product remaining will be recorded via a standard form. The study team will record if the subject was not able to tolerate or receive the full dose due to adverse events or because the allowed duration of administration was exceeded.

5.9. *Return or Destruction of Investigational Product*

For PMT-001 or PMT-002, the volume of investigational product will be recorded at the time of drug product manufacturing, and the volume of residual investigational product (if any) will be recorded by the licensed medical professional performing administration after administration is completed (or stopped). For PMT-003, the number of capsules in the dose will be recorded at the time of drug product manufacturing, and the number of remaining capsules (if any) will be recorded by the licensed medical professional performing administration after administration is completed (or stopped). Any remaining investigational product will be disposed of at the clinical site.

6. Study Procedures

The study procedures are also outlined in detail below. The schedule of study procedures is presented in [Table 2](#).

6.1. *Screening and Enrollment*

6.1.1. *Surveillance Test Review*

Potential subjects will be identified by active screening or referral for FMT treatment at participating study sites.

6.1.2. *Medical Record Review for Inclusion/Exclusion Criteria*

Referral for FMT treatment will prompt review of the electronic health record to determine whether a potential subject may meet inclusion/exclusion criteria ([Sections 4.1](#) and [4.2](#)).

6.1.3. *Informed Consent*

If a potential subject may meet inclusion/exclusion criteria, the study team will contact the potential subject (or their designated medical decision-maker) to discuss participation. If the potential subject is eligible and wants to participate, informed consent will be obtained. Subjects of childbearing potential will be tested using a urine pregnancy test if possible; if urine pregnancy test positive or not possible, potential subjects will be excluded. A record of all screened subjects will be maintained to evaluate the frequency of identified exclusions or care-team objections.

6.1.4. Decision on Mode of Delivery

The enrolled subject will be offered PMT-001, PMT-002, or PMT-003, so long as the enrolled subject and their referring care provider deem the modes of delivery safe. The decision on mode of delivery will be determined by subject preference.

6.1.5. Randomization

Following enrollment and the subject's decision on mode of delivery, stratified randomization will be performed as per [Section 3.1.5](#).

6.2. *Study Intervention Phase*

6.2.1. PMT Product Receipt

After the treatment plan is determined by randomization, the PMT product to which the subjects is assigned will be prepared and received as described above ([Sections 5.2 - 5.7](#)).

6.2.2. Administration

During the intervention period, following informed consent and randomization, subjects will receive either (1) single-dose PMT administration alone, or (2) one-dose PMT administration followed by a second dose within 24 hours (with at least 4 hours separating doses). Each administration of the product (PMT-001, PMT-002, or PMT-003) will take place over 10 to 90 minutes (target 30 minutes). Antibiotics prescribed as part of routine clinical care for CDI will be stopped 12-48 hours (target 24 hours) prior to the intervention.

6.2.3. Post-Intervention 60 minutes

Subjects will be monitored for a period of 60 minutes following completion of each PMT administration. Subjects will be visually observed for signs of aspiration or other respiratory distress, abdominal pain, vomiting, other signs of allergic reaction, and changes in vital signs. Vital signs (temperature, heart rate, respiratory rate, blood pressure, and oxygen saturation) will be checked immediately post-administration and at 30 and 60 minutes following completion of PMT administration. The following vital sign changes will be recorded if observed, and will prompt notification of the primary clinical care team: (1) increase or decrease by greater than or equal to 30 beats per minute; (2) respiratory rate increase or decrease by greater than or equal to 10 breaths per minute or if respiratory rate drops below 10 or increases above 25 (if respiratory rate not already outside these ranges); (3) temperature: increase or decrease by greater than or equal to 2 degrees Fahrenheit, or if temperature drops below 96°F or increases above 100.4°F (if temperature not already outside these ranges); (4) oxygen saturation decrease by greater than or equal to 5% (sustained for more than 20 seconds) or if oxygen saturation drops below 90% (on current amount of oxygen delivered, sustained for more than 20 seconds); (5) blood pressure decrease by more than 30 mmHg systolic or 15 mmHg diastolic, or if blood pressure drops below 90/60 (if blood pressure not already outside these ranges).

6.3. Study Follow-up Phase

6.3.1. Follow-up 7 days

Following a subject's final PMT administration, subjects enter the follow up phase. During this phase, vital signs, symptoms, and laboratory values suggestive of adverse events will be tracked and recorded. Specifically, while remaining inpatient, daily maximum temperature, number of bowel movements, and any episodes of emesis will be recorded (based on electronic medical record) for 7 calendar days post-FMT. In preparation for discharge, subjects will be given a diary for tracking daily temperature, number of bowel movements, and any episodes of emesis for 7 days post last FMT (all subjects will be given a symptom diary card; a digital thermometer will also be provided). Subjects will be contacted by telephone or in-person for an interview focused on potential adverse events at 7 days after final FMT; the first attempt at contact will be made by the first working day at 7 days or later (not to exceed 10 days) following the final FMT. (In case of telephone follow-up, the 7-day symptom diary card will be transcribed by study staff over the phone/and or collected during the in-person follow-up visit. See [Section 6.3.2](#)). Telephone versus in-person follow-up will be determined based on subject preference. If subjects prefer to be seen in person, but have been discharged from the hospital, a clinic visit with a study team member will be arranged.

To address the exploratory aims, if blood that was collected for clinical purposes would otherwise be discarded, it will be captured for immune response phenotyping. Blood will be collected from residual material available in EDTA ("purple top") vacutainer tubes already collected in the clinical laboratory. If no residual blood is available, or if subjects are outpatients or have been discharged from the hospital, no blood will be collected. Blood specimen analysis will be directed by the principal investigator and study team.

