3.2. Study Endpoints

3.2.1. Primary Study Endpoints

The primary endpoint will be proportion of subjects with clinical resolution of diarrhea without recurrence in subjects with R-CDI at 8 weeks (56 days) following FMT. Clinical resolution will be defined as follows:

- ≤ 4 stools per calendar day for the prior two days with no stool of Bristol stool scale type 7
- No additional stool tests with a positive EIA for *C. difficile* toxin since study enrollment
- No additional prescription or use of anti-CDI antibiotics (unless given for prophylaxis) since study enrollment
- No need for an additional FMT administration since study enrollment
- Subject is alive

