3.2.2. Secondary Study Endpoints

Secondary endpoints include:

- All-cause mortality at 30- and 60-days following last FMT
- Colectomy or diverting ileostomy within 30 days after last FMT
- Cumulative days of hospitalization from enrollment until 30 days after FMT
- Cumulative days in intensive care unit from enrollment until 30 days after last FMT
- Bacteremia from enrollment until 30 days after last FMT
- Hospital admission within 60 days of discharge from index hospitalization

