6.3.3. Follow-up 56 days

Subjects will be contacted by telephone or in-person at 56 days (+/- 7 days) after final FMT for an interview focused on the primary outcome and potential adverse events. Telephone versus in-person follow-up will be determined based on subject preference. (If subjects prefer to be seen in person, but have been discharged from the hospital, a clinic visit with a study team member will be arranged).

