Subjects may withdraw from the study at any time without impact to their regular medical care, but they will receive no further treatment with investigational product. They may also be discontinued from the study at the discretion of the Investigator for lack of adherence to intervention or study procedures or visit schedules, adverse events, or due to other concerns. The Investigator or the Sponsor may withdraw subjects who violate the study plan, or to protect the subject for reasons of safety or for administrative reasons. It will be documented whether or not each subject completes the clinical study. The targeted study enrollment is 300 subjects randomized; subjects who withdrawal after randomization will not be replaced.

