8.4.2. Efficacy Analysis

An intention to treat analysis will be performed for the primary outcome of clinical resolution of diarrhea without recurrence in subjects with R-CDI at 8 weeks following FMT. A logistic regression model will be used to compare the two study groups (single-dose versus double-dose) to detect superiority of a dose. A p-value (one-sided) of <0.2 will be considered significant. As above, the primary analysis will be stratified based on the most recent positive CDI test (NAAT versus EIA) prior to enrollment. Per protocol analysis will also be performed, based on received (rather than randomized) treatment.

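### Subjects randomized but never dosed have no defined day-56 primary-outcome assessment, although the primary analysis is ITT

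*Combined protocol and SAP*

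**What the plan says.** - **Start of follow-up.** Section 6.3.1, and 3.1.4 in nearly the same words: "Following a subject's final PMT administration, subjects enter the follow up phase".
- **Primary-outcome contact.** Section 6.3.3 places it "at 56 days (+/- 7 days) after final FMT for an interview focused on the primary outcome". The 7-, 30-, 90- and 180-day contacts use the same origin, and Table 2 dates all five visits from the final intervention.
- **Primary endpoint.** Section 3.2.1: "clinical resolution of diarrhea without recurrence in subjects with R-CDI at 8 weeks (56 days) following FMT". It does not say which dose starts the count. One component concerns stool frequency and type over the preceding two days. Three look back to enrollment, for example "No additional prescription or use of anti-CDI antibiotics (unless given for prophylaxis) since study enrollment". The last is being alive. Section 7.7 assesses the criteria by interview and record review.
- **Analysis.** Section 8.4.2: "An intention to treat analysis will be performed for the primary outcome of clinical resolution of diarrhea without recurrence". In 8.5 the sentence on the ITT population is incomplete as it stands, and the statement that all randomized subjects are included is attached to the per-protocol analyses.
- **Order of events.** Section 6.2.1: "After the treatment plan is determined by randomization, the PMT product to which the subjects is assigned will be prepared and received". Randomization thus precedes dosing.
- **Replacement.** Section 6.6: "subjects who withdrawal after randomization will not be replaced".
- **Missing outcomes.** Section 8.3 allows for 10% loss to follow-up. No section says how a missing day-56 outcome enters the analysis.

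**The concern.** An ITT comparison needs the outcome of every randomized subject, or a rule set in advance for those without one. Here the date of the outcome assessment depends on an event after randomization, the final administration. A subject for whom that event never happens has no date for the interview.

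The gap concerns subjects who receive no dose at all. A double-dose subject who receives only one dose still has a final administration, and so has a visit schedule.

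The trial is open label (5.6), so the assigned arm is known before dosing. The decision not to go ahead can therefore depend on the arm and on how the patient is doing. If undosed subjects are left out, the comparison loses some of the protection of randomization. If they are kept, someone must decide how to classify them, and without a written rule that decision could be made after the results are known.

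**Working it through.** **1. Do other provisions supply the assessment?**

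| Provision | What it gives an undosed subject | What it leaves open |
|---|---|---|
| 8.4.4: adverse events in all randomized subjects from enrollment | Safety data | The efficacy endpoint |
| 6.6.2: on withdrawal, activities of the next scheduled visit are requested | One contact | No next visit is dated without a dose, and one early contact is not a day-56 assessment |
| 3.1.4 and 6.3.5: record review for subjects lost after three failed contacts | Toxin tests, prescriptions, repeat FMT, vital status | No day-56 date; weak source for the stool component |
| 6.6.1: consent withdrawn | Data up to withdrawal | Nothing further can be collected |

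If all components of 3.2.1 are required, a record can establish failure, since one failed component is enough. It can hardly establish success, which also needs the stool history. Record review alone would therefore lean towards failure for these subjects.

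**2. The plan's own power figure (8.3).** Inputs: 300 subjects; 150 x 0.9 = 135 evaluable per arm; split 1:2 into 45 (EIA) and 90 (NAAT); two-sided alpha 0.2; 50% against 71.33% (EIA) and 65.43% (NAAT).

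Power = Phi( (p2 - p1) / sqrt[ p1(1-p1)/n + p2(1-p2)/n ] - 1.2816 )

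- NAAT: 0.1543 / sqrt(0.2500/90 + 0.2262/90) = 2.121; less 1.2816 = 0.840; power 0.80.
- EIA: 0.2133 / sqrt(0.2500/45 + 0.2045/45) = 2.122; less 1.2816 = 0.841; power 0.80.

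Both stated figures reproduce.

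**3. Effect of undosed subjects on power.** The documents give no rate. Assume a share u, equal in both arms and additional to the 10% loss. If these subjects are dropped, n becomes n(1-u). If they are counted as not resolved, both cure rates are multiplied by (1-u).

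| u | Subjects of 300 | Dropped, EIA / NAAT | Counted as failures, EIA / NAAT |
|---|---|---|---|
| 0 | 0 | 0.800 / 0.799 | 0.800 / 0.799 |
| 2% | 6 | 0.794 / 0.793 | 0.784 / 0.785 |
| 5% | 15 | 0.784 / 0.784 | 0.760 / 0.763 |
| 10% | 30 | 0.768 / 0.768 | 0.720 / 0.726 |

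If the undosed fall within the existing 10% allowance and are dropped, power does not change.

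**4. Worst-case effect on the comparison.** If 5% of one arm is unassessed (0.05 x 150 = 7.5 subjects), that arm's cure rate can lie anywhere in a 5-point range. If the same share applies within the NAAT group, that is 5/15.43 = 0.32 of its planned difference. Under the one-sided 0.2 threshold of 8.4.2, a NAAT result near 50% becomes significant at about 0.84 x sqrt(2 x 0.25/90) = 0.063, or 6.3 points. The 5 points are a bound, not an expected bias.

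**5. Timing between the arms.** The second dose comes 4 to 24 hours after the first (3.1.2), so the double-dose clock starts at most 1 day later: 1/56 = 1.8% of the interval, inside a window of +/-7 days. Under an assumed constant failure hazard, one extra day lowers a 50% cure rate by 0.50 - 0.50^(57/56) = 0.6 points and a 70% rate by 0.70 - 0.70^(57/56) = 0.4 points.

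**The case against.** The strongest reply is that few subjects will go undosed. A product that exceeds its time limit is destroyed and another dose is offered (5.4). The route is chosen before randomization, and a subject who cannot take half a dose may switch route (3.1.2, 5.2). Table 2 puts randomization and intervention on the same study day, which leaves little time for deterioration or a change of mind. This stands as an argument about number: it removes the likeliest logistic causes, but not withdrawal or a clinical change before the first dose.

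It can also be said that three endpoint components look back to enrollment and need no dosing date, and that visit timing does not redefine an analysis stated to be ITT. Both are correct. A reader might infer that undosed subjects have no data at all, or that the plan has become an analysis of dosed subjects only. The documents do not support either reading: adverse events and records are available, and ITT is stated. What is lacking is a defined day-56 assessment and a rule for its absence.

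A reader might also infer that the arms run on materially different clocks. They do not. One rule, the subject's own final dose, serves both arms, and the offset is at most a day. Among the cumulative-day endpoints in 3.2.2, only ICU days are tied to the last dose ("Cumulative days in intensive care unit from enrollment until 30 days after last FMT"). Hospital days are counted to 30 days after FMT, with no dose specified. The ICU window is longer by at most 1/30 = 3.3%, which is a window length and not a bias.

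**Conclusion.** The point holds for subjects who are randomized and receive no PMT. The schedule gives them no day-56 assessment, the partial provisions do not supply the interview-based stool component, and no rule classifies the missing outcome. It should be corrected, because the interview cannot be reconstructed later.

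The size is unknown and probably small. The figure of 6-15 of 300 rests on an assumed 2-5% rate, and the power loss at that rate is at most about 4 points. Whether non-dosing would differ by arm is also not known; the open-label design makes it possible. Nothing here calls for changing the visit timing of dosed subjects.

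**What to change.** - **3.1.4, 6.3 and Table 2:** state that a randomized subject who receives no PMT is followed from the date of randomization, with the same day 7 to 180 contacts and record review, unless consent is withdrawn. Since Table 2 places randomization and intervention on the same day, these dates are comparable with those of dosed subjects.
- **8.4.2 and 8.5:** define the ITT population as all randomized subjects in their assigned arm. State how an unassessed day-56 outcome is classified, for example as not resolved, with a sensitivity analysis under another assumption. This rule also covers those who withdraw consent, whom extra follow-up cannot reach.
- **3.2.2 and 8.2:** use *FMT* or *last FMT* consistently.

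The cost is a wording amendment and a few extra telephone contacts. Visits for dosed subjects stay where they are.

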6.3.2. Follow-up 30 days

Subjects will be contacted again by telephone or in-person at 30 days (+/- 3 days) after final FMT for an interview focused on potential adverse events. Telephone versus in-person follow-up will be determined based on subject preference. Subjects enrolled as outpatients will have at least one in-person follow-up visit scheduled between 1- and 4 weeks post-FMT. (If subjects prefer to be seen in person, but have been discharged from the hospital, a clinic visit with a study team member will be arranged).

6.3.3. Follow-up 56 days

Subjects will be contacted by telephone or in-person at 56 days (+/- 7 days) after final FMT for an interview focused on the primary outcome and potential adverse events. Telephone versus in-person follow-up will be determined based on subject preference. (If subjects prefer to be seen in person, but have been discharged from the hospital, a clinic visit with a study team member will be arranged).

6.3.4. Follow-up 90 days

Subjects will be contacted by telephone or in-person at 90 days (+/- 7 days) after final FMT for an interview focused on potential adverse events. Telephone versus in-person follow-up will be

determined based on subject preference. (If subjects prefer to be seen in person, but have been discharged from the hospital, a clinic visit with a study team member will be arranged).

6.3.5. End-of-study visit at 180 days

The study will conclude after subjects are contacted by telephone or in-person at 180 days (+/- 10 days) after final FMT for a final interview focused on potential adverse events. Telephone versus in-person follow-up will be determined based on subject preference. (If subjects prefer to be seen in person, but have been discharged from the hospital, a clinic visit with a study team member will be arranged).

Subjects will be permitted to initiate electronic communication with the study team, although planned follow up visits will be conducted by telephone or in person. The study team may reach out to subjects electronically if difficulties arise in reaching the subject by telephone in order to schedule visits, but study-related questions will not be asked electronically. Subjects will be classified as lost to follow up if at least three attempts are made at contact without success; however, medical record review will still be used to obtain follow up information on these subjects. If a subject is eligible and enrolled a second (or greater) time, then their subsequent follow up will be conducted according to the schedule set by their most recent enrollment, and any remaining follow ups from earlier enrollment(s) will not be performed.

6.4. *Rescue Therapy*

If a subject is thought to have a severe adverse event it will be recorded by the study team and the subject will be followed until resolution and referred to subject's primary clinical care team. In the case of an inadequate clinical response, the subject's primary clinical care team will be contacted, so that the subject can pursue treatment at their discretion. Regardless of rescue therapy used, subjects will continue to be followed until the end of the study.

6.5. *Unscheduled Visits*

Data collected from subjects who contact the study team (by telephone, electronically, or in-person) outside of the scheduled visits (as above) will be associated with the next scheduled study visit, as each study visit is intended to retrospectively cover the time period since the last study visit.

6.6. *Subject Withdrawal*

Subjects may withdraw from the study at any time without impact to their regular medical care, but they will receive no further treatment with investigational product. They may also be discontinued from the study at the discretion of the Investigator for lack of adherence to intervention or study procedures or visit schedules, adverse events, or due to other concerns. The Investigator or the Sponsor may withdraw subjects who violate the study plan, or to protect the subject for reasons of safety or for administrative reasons. It will be documented whether or not each subject completes the clinical study. The targeted study enrollment is 300 subjects randomized; subjects who withdrawal after randomization will not be replaced.

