Telephone versus in-person follow-up will be determined based on subject preference. (If subjects prefer to be seen in person, but have been discharged from the hospital, a clinic visit with a study team member will be arranged). Subjects enrolled as outpatients will have at least one in-person follow-up visit scheduled between 1- and 4-weeks post-FMT. All FMT recipients (or their surrogates) will be given contact information for the study coordinator. As detailed above, subjects will be followed for 180 days following last investigational product administration. All subjects will be also provided a study contact telephone number on a copy of the informed consent form, in case concerns for adverse event or other questions arise. Subjects will also be permitted to initiate electronic communication with the study team, although planned follow up visits will be conducted by telephone or in person. The study team may reach out to subjects electronically if difficulties arise in reaching the subject by telephone in order to schedule visits, but study-related questions will not be asked electronically. Subjects will be classified as lost to follow up if at least three attempts are made at contact without success; however, medical record review will still be used to obtain follow up information on these subjects. If a subject is eligible and enrolled a second (or greater) time, then their subsequent

follow up will be conducted according to the schedule set by their most recent enrollment, and any remaining follow ups from earlier enrollment(s) will not be performed.

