4.1. Inclusion Criteria

1. Second or greater episode of CDI (first or greater recurrence) within 12 months, with symptoms including bowel movement altered in frequency or consistency from baseline.
2. Stool positive for *C. difficile* toxin by EIA or toxin gene by NAAT within 60 days of enrollment.
3. At least one additional prior positive stool test for *C. difficile* within the prior 12 months (EIA or NAAT as above).
4. Age \geq 18 years.
5. Minimum of 72 hours of receipt of standard-of-care (vancomycin or fidaxomicin) antibiotic treatment for R-CDI prior to intervention.

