4.2. Exclusion Criteria

1. Evidence of colon/small bowel perforation at the time of study screening
2. Goals of care are directed to comfort rather than curative measures.
3. Moderate (ANC < 1000 cells/uL) or severe (ANC < 500 cells/uL) neutropenia.
4. Known food allergy that could lead to anaphylaxis.
5. Pregnancy
 - a. For subjects of childbearing potential (ages 18 to 55), the subject must have a negative urine pregnancy test within 48 hours of consent and no more than 48 hours prior to first product administration
6. Meeting criteria for severe, severe-complicated/fulminant CDI within 24 hours of planned trial enrollment. We define severe or severe-complicated/fulminant CDI as any one of the following: (1) leukocytosis with peripheral WBC $\geq 15,000$ cells/mL; (2) hypotension with systolic blood pressure sustained < 90 mmHg for three or more hours or requiring pressors; (3) provider documentation of ileus or radiologic evidence of bowel dilation or megacolon;

(4) acute kidney injury with increase in baseline serum creatinine level by $\geq 50\%$ or new dialysis initiation; (5) serum lactate > 2.2 mmol/L; or (6) ≥ 3 systemic inflammatory response syndrome (SIRS) criteria (which include heart rate > 90 beats per minute, respiratory rate > 20 breaths per minute or $\text{PaCO}_2 < 32$ mmHg, temperature $> 38^\circ\text{C}$ or $< 36^\circ\text{C}$, $\text{WBC} > 12,000$ cells/uL, $< 4,000$ cells/uL, or $> 10\%$ immature (band) forms).

7. Receipt of FMT or enrollment in a clinical trial for FMT within the last 3 months.

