- sepsis or shock (temperature, heart rate, or blood pressure change as already described) – PMT-001, 002, and 003
- bowel injury (abdominal pain change as already described) – PMT-001, 002, and 003

- aspiration (respiratory rate or oxygen saturation change as already described) – PMT-002 and 003 only

In the subsequent, 7-day monitoring period following administration of investigational product, subjects will be monitored with close attention to the following:

- donor-derived infection (temperature or abdominal pain change as already described) – PMT-001, 002, and 003
- worsening CDI (temperature, change in stool frequency/quantity or abdominal pain, or emesis as already described) – PMT-001, 002, and 003

In the subsequent, 30-, 56-, 90-, and 180-day monitoring periods, subjects will be monitored with close attention to the following:

- transmitted infection (temperature or abdominal pain change as already described) – PMT-001, 002, and 003
- recurrent CDI (temperature, change in stool frequency/quantity or abdominal pain, or emesis as already described) – PMT-001, 002, and 003
- metabolic changes (polydipsia, polyuria, weight gain or weight loss) – PMT-001, 002, and 003

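### Re-enrollment cancels the outstanding late safety visits of the first randomization only in subjects who relapsed, and no rule says how a person randomized twice is counted or analysed

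*Combined protocol and SAP*

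**What the plan says.** Sections 3.1.4 and 6.3.5 carry the same rule. It opens "If a subject is eligible and enrolled a second (or greater) time", moves the subject to the schedule of the newest enrollment, and ends "any remaining follow ups from earlier enrollment(s) will not be performed". There is no limit on the number of enrollments, and no separate randomization procedure for repeats, so a returning subject is randomized 1:1 as in Section 3.1.5.

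Two criteria govern when this can happen. Exclusion 7 (Section 4.2) bars "Receipt of FMT or enrollment in a clinical trial for FMT within the last 3 months". Section 4.1 requires a second or later symptomatic episode and stool positive for "toxin by EIA or toxin gene by NAAT within 60 days of enrollment".

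Frequency of AESIs and of SAEs are primary safety endpoints (Section 3.2.3). Section 9.1.3 lists among the AESIs for the 30-, 56-, 90- and 180-day periods "recurrent CDI (temperature, change in stool frequency/quantity or abdominal pain, or emesis as already described", along with transmitted infection and metabolic change. Section 6.5 makes each visit cover the time since the previous one and attaches unscheduled reports to the next scheduled visit. Section 7.1 ties post-baseline record review to the same visits.

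Sections 6.6 and 8.3 speak of 300 subjects, 150 per arm. The logistic model in Section 8.4.2 has no term or variance adjustment for a person who appears twice. Section 8.5, whose primary-analysis sentence is incomplete, does not mention repeat entries.

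**The concern.** Two things are at stake.

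The first is late safety by randomized arm. Follow-up under the first assignment stops because the subject has relapsed. If one dose strategy leads to more late relapses, that arm loses more of its own late visits. Elsewhere the plan is more careful: Section 6.4 follows rescued subjects to the end of the study, and Section 6.3.5 keeps record review for subjects who cannot be reached. A re-enrolled subject, who is still in contact, gets less first-enrollment follow-up than either.

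The second is the unit of analysis. A second entry belongs to a person who has already received one or two PMT doses, possibly under the other arm, and who was selected for recurrence. The plan does not say whether that entry counts toward the 300, enters the ITT set, or is adjusted for earlier exposure. In an open-label trial with a threshold of 0.2, that choice should not be left until the data are in.

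**Working it through.** **1. Which first-enrollment visits can be lost.** All days are counted from the final FMT of the first enrollment.

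- Earliest re-entry: 3 months = 365.25/4, about day 91 (exclusion 7).
- Primary visit: "Subjects will be contacted by telephone or in-person at 56 days (+/- 7 days) after final FMT" gives a latest day of 56 + 7 = 63. Since 63 < 91, no primary outcome of the first randomization is lost.
- Day-90 visit: "Subjects will be contacted by telephone or in-person at 90 days (+/- 7 days) after final FMT" gives days 83-97. Only a visit still outstanding at about days 91-97 can be cancelled.
- Day-180 visit: 180 ± 10 in Section 6.3.5 gives days 170-190 (Section 3.1.4 says ± 7). It is cancelled if re-entry comes first. Re-entry after it cancels nothing.

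**2. What the new schedule covers.** Re-entry at day 91 puts the new 90-day contact at 91 + 90 = day 181, inside 170-190, and the new 180-day contact at day 271. Calendar observation therefore continues past the original day 180. For re-entry at day 150 the new 30-day contact falls on day 180. But days 90-150 precede the new dose, and the only first-enrollment visit meant to cover them was the cancelled day-180 contact. The record review done at re-entry is for eligibility (Section 7.1). Nothing in the plan assigns the qualifying recurrence, or anything after it, to the first arm.

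**3. The plan's power figures.** With power = Φ(|p2 − p1| / √[(p1q1 + p2q2)/n] − z), p1 = 0.50 and two-sided alpha 0.2 (z = 1.2816), as in Section 8.3:

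- EIA, n = 45, p2 = 0.7133: 0.2133/√(0.4545/45) = 2.122; 2.122 − 1.282 = 0.841; power 0.800.
- NAAT, n = 90, p2 = 0.6543: 0.1543/√(0.4762/90) = 2.121; 2.121 − 1.282 = 0.840; power 0.799.

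Both reproduce the stated 80%, as do the other four rows of the table.

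**4. Cost if repeats fill the 300 but only first entries are analysed.** The documents give no re-enrollment rate, so the shares below are assumptions; n is multiplied by (1 − share).

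| Repeat share | n per arm, EIA / NAAT | Power, EIA / NAAT | Detectable difference, EIA / NAAT |
|---|---|---|---|
| 0% | 45 / 90 | 0.800 / 0.799 | 0.213 / 0.154 |
| 2% | 44.1 / 88.2 | 0.794 / 0.793 | 0.215 / 0.156 |
| 5% | 42.8 / 85.5 | 0.784 / 0.784 | 0.218 / 0.158 |
| 10% | 40.5 / 81 | 0.768 / 0.768 | 0.224 / 0.162 |

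**5. Effect if repeats are analysed as independent.** Simulation of 180 NAAT records, 8,000 runs per setting, 5% or 10% repeats drawn from failures and late relapsers, independent re-randomization, within-person correlation 0 or 0.5, no carry-over.

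| | With repeats | Without repeats |
|---|---|---|
| Type I error, two-sided 0.20 | 0.202-0.206 | 0.203-0.206 |
| Type I error, one-sided 0.20 (the Section 8.4.2 rule) | 0.203-0.217 | 0.207-0.208 |
| Power, two-sided | 0.79-0.80 | 0.80 |

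The Monte Carlo standard error is √(0.2 × 0.8/8000) = 0.0045. The highest one-sided value, 0.217, arose at 5% repeats with correlation 0.5; at 10% with the same correlation it was 0.203, so error does not rise with the share of repeats.

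**The case against.** The case against is substantial, and most of it limits the point.

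A reader might infer that late recurrences are lost. They are not: the relapse behind re-entry must be known to the study, because eligibility requires symptoms and a recent positive test, and Section 9.3 keeps adverse-event reporting open from consent to study completion. What is missing is its assignment to the first arm.

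A reader might also infer that day 180 is always dropped, or that about half of the 180 days goes unobserved. The dates contradict both. After the new dose the difficulty is attribution, since an event could belong to either enrollment; completing the old visit does not remove that, and such events can only be flagged.

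It is tempting to say that the dose comparison is biased. Re-randomization balances earlier exposure and selection for relapse in expectation, and the simulation shows no meaningful damage. It did not include carry-over, so this is absence of demonstrated harm rather than proof of none.

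Nor can the number of repeats be derived from the planned cure rates. Failures include deaths, an FMT given as rescue restarts the 3-month exclusion, and a positive test from an early failure can age out of the 60-day window.

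Finally, Section 8.4.4 only describes safety frequencies, and 300 subjects ordinarily means 300 persons. Both are fair. But a descriptive 180-day frequency is still incomplete if its visits stop on relapse, and the ordinary meaning does not settle whether a second randomization enters the model. One could read exclusion 7 as barring anyone still in follow-up, so that nothing would ever be cancelled; but the re-enrollment rule itself foresees outstanding visits, so that reading fits poorly.

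**Conclusion.** The point holds in limited form. The first randomization's primary outcome is protected by the 3-month exclusion. For subjects who re-enter between about day 91 and their day-180 visit, the plan drops first-enrollment late follow-up selectively in relapsers, leaves the interval before re-entry without a first-enrollment visit or review, and assigns neither the qualifying recurrence nor later events to the first arm. Late AESI and SAE frequencies by arm are therefore incomplete in a way that depends on outcome. How many subjects this affects cannot be derived from the documents.

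For the primary comparison the defect is an undefined unit of analysis, not a demonstrated inflation of error. The numerical cost is small: about 0.02 to 0.03 of power at 5-10% repeats (assumed) if repeats use up places in the 300, and none if the 300 are unique persons. The change should be made, mainly for the sake of late safety by randomized arm.

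**What to change.** 1. In Sections 3.1.4 and 6.3.5, replace the sentence that cancels earlier follow-up. On re-enrollment, review the interval since the last completed visit; record the qualifying recurrence as a recurrent-CDI AESI against the first-randomized arm; and complete the outstanding day-90 and day-180 checks of the first enrollment, using contacts and record reviews of the new schedule where they coincide. Flag events after the new dose.

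2. In Sections 8.3 to 8.5, base the primary ITT and safety-by-arm analyses on each person's first randomization and define the 300 as unique persons. Report repeat entries separately, or in a supportive analysis with variance clustered by person and a term for earlier PMT exposure.

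The cost is a few sentences in the protocol and analysis plan and a small number of record reviews or calls, many of which coincide with contacts already planned. The drawback is that repeat entries no longer count toward the 300, so recruitment must supply that many different people.
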